4.1 Number of Patients

Approximately 76 patients will be enrolled at approximately 25 sites in the US and Canada to achieve 72 evaluable patients (N = 36, N = 18, and N = 18 in the 3 treatment groups, respectively) based on an anticipated dropout rate of 5%.

4.2 Study Population Characteristics

The study population will consist of adult female patients with a history of IC with HL along with the associated symptoms as previously reported in guidelines by van de Merwe et al (2008).

4.3 Inclusion Criteria

The following are requirements for entry into the study:

5. A diagnosis of IC with HL defined as:

an unpleasant sensation (pain, pressure, discomfort) perceived to be related to the urinary bladder, associated with lower urinary tract symptoms (LUTS) of more than 6 months duration in the absence of infection or other identifiable causes (van de Merwe et al, 2008), documented history or patient reported

and

• documented history of an observation of HL via cystoscopic procedure in which a lesion is defined as a circumscript, reddened mucosal area that can be small vessels radiating towards a central scar, and/or a fibrin deposit of coagulum attached to this area. Lesions may also be linear, fissure-like, and may be bleeding.

Exclusion Criteria 4.4

The following are criteria for exclusion from participating in the study:

- 1. Patient who is pregnant, nursing, or planning a pregnancy during study participation
- 2. Patient of childbearing potential who is unable or unwilling to use a reliable form of contraception during the study (as defined in Section 4.5.1.1)

		_
_		
	27	GDD-TA-T-004 v2013.9

_
—
-
_
-

19. Previous exposure to LiRIS in a TARIS clinical study within 6 months prior to Screening.

4.5 Permissible and Prohibited Medications/Treatments

4.5.1 Permissible Medications/Treatments

Therapy considered necessary for the patient's welfare may be given at the discretion of the investigator. Patient should be instructed to maintain a stable dose of chronic medications during the study whenever possible. Please see Table 2 for a list of permissible medications with the required stable duration prior to Screening (if continuing as stable therapy in the study), the period off medication/treatment prior to Screening, and permissible short-term rescue therapy (medication must have been used previously, prior to study entry with no tolerability issues). See Section 4.5.3 regarding rescue medication.

All medications, adjunct therapies, and concurrent procedures should be recorded on the appropriate electronic case report form (eCRF). If the permissibility of a specific medication/treatment is in question, please contact the assigned Medical Safety Physician of the study.

4.5.1.1 Definition of Females of (Non)Childbearing Potential and/or Acceptable Contraceptive Methods

For purposes of this study, females will be considered of childbearing potential unless they are naturally postmenopausal or permanently sterilized (ie, hysterectomy). Natural menopause is defined as the permanent cessation of menstrual periods, determined retrospectively after a woman has experienced 12 months of amenorrhea without any other obvious pathological or physiological cause. For women of childbearing potential who may participate in the study, the following methods of contraception, if properly used, are generally considered reliable: hormonal contraceptives (ie, oral, patch, injection, implant), male condom with intravaginal spermicide, diaphragm or cervical cap with spermicide, vaginal contraceptive ring, intrauterine device, surgical sterilization (bilateral tubal ligation, bilateral salpingectomy), vasectomized partner, or total sexual abstinence (when this is in line with the preferred or usual lifestyle of the patient).

The investigator and each patient will determine the appropriate method of contraception for the patient during the participation in the study.

If a female becomes pregnant during the study, the investigator will notify Allergan immediately after the pregnancy is confirmed and the patient will be exited from the study after appropriate safety follow-up. The investigator will (1) notify the patient's physician that the patient was being treated with an investigational drug LiRIS 400 mg or LiRIS Placebo, and (2) follow the progress of the pregnancy. The investigator must document the outcome of the pregnancy and provide a copy of the documentation to the Medical Safety Physician assigned to this study.

4.5.2 Prohibited Medications/Treatments

Use of the following medications/treatments is prohibited throughout study participation:

• botulinum toxin treatment of any serotype for any genitourinary indication

• patients who are not on a stable dose of any oral medications/physical therapy (see Table 2) for the treatment of IC should not use them for the duration of the study unless they are being used as a rescue medication (Section 4.5.3)

Note: Possible effects on study safety and endpoints should be taken into consideration when initiating treatment during the trial with any of the oral medications listed in Table 2 for an indication outside of IC.

- any intravesical pharmacotherapies (eg, dimethyl sulfoxide [DMSO], sodium hyaluronate [Cystistat[®]], chondroitin [Uracyst[®]], pentosan polysulfate sodium [Elmiron[®]], heparin, lidocaine, sodium bicarbonate, capsaicin or resiniferatoxin)
- use of electrical stimulation or neuromodulation devices (implanted and external) for the treatment of LUTS or pain. If a patient is enrolled into the study with a device still implanted, it must be inactive for 4 weeks prior to treatment on Randomization/Day 0 and must remain inactive for the duration of the study
- hydrodistention (or any other procedure that may result in bladder distention)
- general or spinal anesthesia may not be administered at the same time as the IP insertion/removal
- products other than IP that would result in systemic lidocaine exposure (eg, lidocaine patch [Lidoderm], IV lidocaine, intrathecal lidocaine)

The decision to administer a prohibited medication/treatment is done with the safety of the study participant as the primary consideration. When possible, the assigned Medical Safety Physician for this study should be notified before the prohibited medication/treatment is administered.

4.5.3 Rescue Medications

Use of confounding medications should be minimized in the study and avoided if possible, however rescue medications may be used on an as needed, short-term basis according to local site practice for patients who have an acute exacerbation of pain ("flare") (Table 2). The following medications may be used:

• any oral pain relieving medication (except herbal medications) that the patient has previously used for IC within the 3 months prior to Screening and has been tolerated

Use of any nonpain relieving medications (eg, anticholinergics) is prohibited as rescue medication.

All usage of rescue medication should be recorded (time of use and dose) on the pain diary by the patient and on the appropriate eCRF by the site staff. In addition sites should question patients at all visits regarding the use of rescue medications between visits and any such usage should be recorded in the appropriate eCRF.

4.5.4 Oral Prophylactic Antibiotics

Oral prophylactic antibiotics use before and after cystoscopy procedures are recommended and should be used per local site practice. Patients shall begin oral prophylactic antibiotics 3 days prior to, on the day of, and following the procedure, for 3 days .

Any oral antibiotics approved for the treatment of UTIs may be used at the discretion of the investigator and must be recorded on the concomitant medications eCRF.

4.5.5 Study Treatment Anesthesia

Study treatment administration and removal may be performed using local anesthesia (general or spinal anesthesia is prohibited) and/or sedation. The type of anesthesia used is at the investigator's discretion, depending on the patient's expected tolerability and available facilities.

One or more of the following options are permitted as per local site practice:

- local anesthesia or lubricating gel to the urethra to facilitate cystoscope insertion
- sedatives (oral or IV) may be administered

All anesthesia should be recorded on the appropriate eCRF.

4.5.6 Special Diet or Activities

[figure not shown]
No restriction on meals or diet is required for this study. Information about patient tobacco use will be collected in order to exclude those patients samples from the 2,6-xylidine analyses. Information about patients dietary lifestyle will be collected (vegan, vegetarian, non-vegetarian).

5. Study Treatments

5.1 Study Treatments and Formulations

The study treatment is LiRIS 400 mg (AGN-201025).

LiRIS is a passive nonresorbable lidocaine-releasing intravesical system whose primary mode of action is the controlled release of lidocaine into the bladder over a 2-week period. The device constituent of LiRIS (both active and placebo) is constructed of medical grade silicone (elastomer) and nitinol wire, which provides the bladder-retentive property of the system.

5.2 Control Treatment

LiRIS Placebo contains lactose minitablets in place of the lidocaine.

5.3 Methods for Masking/Blinding

All study treatments (active and placebo) and packaging will be identical in order to maintain masking of the study. The study treatment will be identified as an investigational compound. The study number and kit number will be identified on the unit label.

5.4 Treatment Allocation Ratio and Stratification

Patients will be randomized centrally and stratified on Randomization/Day 0 by baseline pain score (≤ 5 or > 5). Each patient within a stratification group will be randomized using an automated randomization system to 1 of 3 treatment groups (LiRIS 400 mg/LiRIS 400 mg; LiRIS Placebo/LiRIS Placebo; LiRIS Placebo/LiRIS 400 mg) in a 2:1:1 ratio.

5.5 Method for Assignment to Treatment Groups/Randomization

Following the Screening period, patients who meet the study inclusion/exclusion criteria and day of treatment criteria will be assigned a randomization number through the interactive voice response system (IVRS)/ interactive web response system (IWRS) which determines the treatment group assignment. Study medication will be labeled with medication kit numbers. The IVRS/IWRS system will provide the site with the specific medication kit number(s) for the patient that corresponds to the treatment group to which the patient was assigned. The site will also use IVRS/IWRS to assign a new kit number to each patient who meets Treatment 2 criteria.

5.6 Treatment Regimen and Dosing

5.6.1 Treatment 1

Eligible patients will be randomized on Randomization/Day 0 to receive Treatment 1, LiRIS 400 mg/LiRIS 400 mg; LiRIS Placebo/LiRIS Placebo or LiRIS Placebo/LiRIS 400 mg (Section 5.4). Patients will have the Treatment 1, 1st IP inserted on Randomization/Day 0 and removed on Day 14. On the same day, following the 1st IP removal, the 2nd IP (LiRIS 400 mg or LiRIS Placebo) will be inserted and subsequently removed on Day 28. Patients will be followed for 20 weeks post IP removal for additional safety and efficacy assessments. In the event that a patient does not receive Treatment 2, they will exit the study at Treatment 1 Week 20 Follow-up Visit.

5.6.2 Treatment 2

All patients will receive LiRIS 400 mg for their second treatment. Patients may request, qualify, and receive Treatment 2 IP from Week 4 Follow-up until Week 20 of Treatment 1. In the event that the Treatment 2 IP cannot be inserted on the day of qualification, Treatment 2 may be rescheduled within 14 days of qualification. The LiRIS will be inserted on Treatment 2/Day 0, and will be removed on Day 14. Patients will be followed for 4 weeks post-removal and will be exited from the study.

5.6.3 Premature IP Removal

The IP will be removed immediately and appropriate medical therapy should be instituted immediately, if any of the following occur:

• if patient requests removal of the IP for any reason

- if patient becomes pregnant
- haematuria that is considered by the investigator to be clinically significant
- urinary retention that is considered by the investigator to be clinically significant
- allergic reaction (shortness of breath, generalized edema, etc) to either LiRIS device constituent materials (silicone, nitinol), drug (lidocaine or lactose) and/or excipients (povidone, polyethylene glycol)
- signs of lidocaine toxicity (Xylocaine[®] Injection Package Insert, 2010) where toxicities associated with lidocaine include but are not limited to light-headedness, nervousness, perioral tingling, tingling or numbness of the tongue, confusion, dizziness, drowsiness, tinnitus, blurred or double vision, vomiting, sensations of heat, cold or numbness, twitching, tremors, convulsions, unconsciousness, respiratory depression, respiratory arrest and cardiovascular reactions which are usually depressant in nature and are characterized by bradycardia, hypotension, and cardiovascular collapse, which may lead to cardiac arrest
- a condition or situation that, in the investigator's opinion, may put the patient at significant risk

5.7 Storage of Study Medications/Treatments

The study medication must be stored in a secure area and administered only to patients entered into the clinical study, at no cost to the patient, in accordance with the conditions specified in this protocol.

IP must be stored at room temperature and protected from light, representing a usual and customary working environment. The IP must not be frozen. Sites must report any temperature excursions as described in the Study Manual or contact Allergan or its designee for further instructions.

5.8 Treatment Administration

The insertion, removal, and inspection of the IP are to be completed by the investigator(s) involved with the study. Detailed instructions for the insertion and removal of the IP are in the Study Manual .

5.8.1 Day of Treatment Criteria

The following day of treatment criteria must be fulfilled prior to the administration of study treatment.

- confirm that patient did not have a symptomatic UTI during the baseline pain eligibility criteria assessment period
- negative urine dipstick reagent strip test (for leukocyte esterase and/or nitrites) and, in the investigator's opinion, patient is asymptomatic for a UTI on the day of study treatment
- negative urine pregnancy result (for patients that are of child bearing potential)
- investigator continues to deem treatment is appropriate and no condition or situation exists which, in the investigator's opinion, puts the patient at significant risk from receiving treatment

5.8.2 Qualification for Retreatment

Patients can request retreatment (Treatment 2) at any time from the Week 4 Follow-up clinic visit up through the Week 20 Follow-up clinic visit. A patient will be eligible to receive Treatment 2 (LiRIS 400 mg) only if all of the following criteria are met:

- completed Treatment 1 schedule of visits and procedures from the Week 4 Follow-up visit through qualification, in the opinion of the investigator
- negative urine dipstick reagent strip test (for leukocyte esterase and/or nitrites) and, in the investigator's opinion, patient is asymptomatic for a UTI on the day of study treatment
- negative urine pregnancy result (for patients that are child bearing potential) and are willing to continue using acceptable method of contraception
- Investigator continues to deem treatment is appropriate and no condition or situation exists which, in the investigator's opinion, puts the patient at significant risk from receiving treatment

6. **Response Measures and Summary of Data Collection Methods**

6.1 Efficacy Measures

[figure not shown]
6.1.1 **Primary Efficacy Measure**

[figure not shown]
• average daily bladder pain score patient experienced over the previous 24-hour period as measured by an NRS of 0 to 10, recorded on a 7-day pain assessment tool. The primary timepoint is Week 4 following Treatment 1 2nd IP removal.

6.1.2 Secondary Efficacy Measures

- number of HLs assessed by the PI during cystoscopy
- composite score of HL calculated based on number, size, and severity of the lesions

6.1.3 Other Efficacy Measures

6.4 **Post-use Assessments and Investigational Product Events**

- voiding of the IP
- damage to the IP during insertion or removal procedures
- damage to the IP that is not related to insertion or removal procedures

6.5 Examination Procedures, Tests, Equipment, and Techniques

Screening procedures can commence once the informed consent and data authorization/protection form have been obtained. Screening will be considered to have started (eg, Day -28) at the time of the first Screening activity or procedure. On completion of Screening, when all the required inclusion/exclusion have been met, the patient will be randomized and be considered enrolled into the study.

Evaluations should be performed by the same evaluator throughout the study whenever possible. If it is not possible to use the same evaluator to follow the patient, then it is preferable to have the evaluations overlap (examine the patient together and discuss findings for at least one visit).

6.5.1 Medical History/Demographics

A complete medical history will be obtained and is to include diagnosis or symptom, date of onset, current status, associated surgical procedures, detailed genitourinary history, prior medications/treatments, and reasons for discontinuation. In addition key demographics (ie, information about patients dietary lifestyle [vegan, vegetarian, non-vegetarian], smoker versus non-smoker) will be documented for each patient.

6.5.2 Physical Examination

The physician or appropriately qualified designee will perform a complete physical examination (PE) and examine the patient for any physical abnormalities of the following body systems: head, ears, eyes, nose, and throat (HEENT) and neck, cardiovascular, respiratory, abdomen, musculoskeletal, and skin systems will be performed at the appropriate scheduled visits (see Table 1).

An abbreviated PE includes cardiovascular, respiratory, and abdomen examination. Please refer to Table 1 for the scheduled visit in which the abbreviated PE should be performed compared with a complete PE.

6.5.3 Pelvic Examination

A pelvic examination by a physician investigator should be performed to ensure that the urethra and bladder are palpated last. The initial examination should comprise visual inspection of the external genitalia for signs of infection, tumors, or urethral caruncle, a superficial tactile examination of the external genitalia to elicit superficial non-bladder related tenderness and a careful, gentle palpation of the vulval fourchette and levator ani muscles to assess pelvic floor pain etiology and to rule out high muscle-tone pelvic floor dysfunction as the primary source of the patient's pain. Finally the posterior urethra, bladder neck, and bladder should be palpated to elicit bladder-related pain. This examination must be included as a part of the Screening period PE.

6.5.4 Vital Signs, Weight and Height Measurements

Vital signs will be measured prior to any invasive procedures as outlined below:

- pulse rate (beats per minute): patients should be resting in a seated position
- blood pressure (mm Hg): patients should be resting in a seated position. Systolic/diastolic blood pressure is then measured with a sphygmomanometer.
- temperature (°F or °C): patients should be seated and the body temperature taken according to local site practice
- body weight (Screening and exit) and height (Screening visit only) will be measured according to local site practice

6.5.5 Clinical Laboratory Assessments

All clinical laboratory samples will be analyzed at a central facility. For schedule of blood and urine samples collection, please refer to Table 1.

Analytes will be tested as specified below:

Hematology: red blood cells (RBC); RBC Indices: mean corpuscular volume (MCV), mean corpuscular hemoglobin (MCH), mean corpuscular hemoglobin concentration (MCHC), RBC morphology; white blood cells (WBC); WBC differential (% and absolute): neutrophils, lymphocytes, monocytes, eosinophils, basophils, hematocrit; hemoglobin; and platelets

Blood Chemistry: albumin, alkaline phosphatase, alanine aminotransferase (ALT [SGPT]), aspartate aminotransferase (AST [SGOT]), total and direct bilirubin, blood urea nitrogen (BUN), calcium, chloride, creatinine, gamma glutamyltransferase (GGT), globulin, non-fasting glucose, potassium, total protein, and sodium

Urine Analysis and Urine Culture and Sensitivity: Urinalysis will be performed at all clinic study visits; a urine culture and sensitivity test will also be performed when urinalysis results are suggestive of a potential UTI (positive leukocyte esterase, nitrites, blood and/or microscopic sediments such as WBCs, RBCs, and/or bacteria).

Urine analytes to be tested are listed below:

Urinalysis: Color, appearance, specific gravity; pH, protein, glucose, ketones, occult blood, leukocyte esterase, nitrite, bilirubin, urobilinogen, crystals; microscopic examination if positive for protein, leukocyte, occult blood, nitrite, or crystals

Urine Culture and Sensitivity: Culture, quantitation, isolation, identification, and susceptibility

Urine cytology is performed at the Screening visit only. Abnormal urine cytology suspicious for a urothelial malignancy should be investigated by the investigator according to local site practice, and only if such malignancy is ruled out should the patient be enrolled. Results of the investigation will be recorded in the source documents.

Serum and Urine Pregnancy Test: Beta-human chorionic gonadotropin (β -HCG) performed. Pregnancy testing will be conducted for women of childbearing potential using serum β -HCG test with the exception of any day of IP insertion where urine will be used.

Urine Dipstick Reagent Strip Tests (Urine Dipstick): The urine dipstick is used to identify a potential UTI and to provide immediate information to the investigator.

6.5.6 Pharmacokinetic Analysis Assessments

All enrolled patients will have blood and urine collected for pharmacokinetic analysis of lidocaine and 2,6-xylidine (non-smokers only) during both Treatment 1 and Treatment 2 (if applicable).

Plasma samples will be collected and stored at -20°C or colder until shipped to the central laboratory facility. Detailed instructions for the collection, processing, storage and shipment of samples are provided in the Central Laboratory Manual.

6.5.7 Bladder Post-void Residual

Bladder PVR is to be assessed per the site's standard of care method (eg, bladder scan) but should be performed preferably immediately after voiding. The same method should be consistently used throughout the study. Please see Table 1 for the visits at which PVR should be assessed.

6.5.8 Cystoscopic Examination

All patients will undergo a cystoscopic examination on the days of Insertion of the IP to rule out the presence of any bladder or urethra anatomical feature that, in the opinion of the investigator, might prevent the safe placement, indwelling use, or removal of IP, such as bladder fistulae or stone. In addition, prior to the intial IP insertion on Day 0, the presence of HLs will be confirmed. If during the cystoscopic exam, the investigator discovers an abnormality that would prevent the safe placement, indwelling use, or removal of the IP, the patient will not receive treatment and will be withdrawn from the study.

A brief cystoscopic examination for safety purposes will also be conducted on all patients at the Treatment 1 and Treatment 2 Day of Removal Visits (see Table 1).

During each cystoscopy, the investigator will count the number of lesions visible while performing the bladder scan for bladder mapping.

Investigators may recommend that the patient take pain medication up to 6 hours prior to the cystoscopic procedure and continuing for 24 hours after the procedure to minimize patient anxiety and discomfort.

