7.1 Analysis Populations

The modified intent-to-treat (mITT) analysis population: The mITT population will include all patients who were randomized and received at least 1 IP insertion in Treatment 1. The efficacy data will be analyzed as randomized using the mITT population.

Safety analysis population: The safety population will include all patients enrolled in this study and received at least one IP. The safety data will be analyzed as treated using the safety population.

Pharmacokinetic evaluable population: The pharmacokinetic population will include all patients enrolled in this study and who have at least one plasma or urine pharmacokinetic concentration measurement post-IP insertion and for whom the IP is successfully removed.

Per-protocol (PP) analysis population: The PP population will include all patients who retain the 2 IP inserted in Treatment 1 for the 28 days of the treatment period and complete the 4 Week Follow-up Visit post removal of the 2^{nd} IP of Treatment 1 without any significant protocol deviations. Protocol deviations will be determined prior to database lock.

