8.7 Early Discontinuation of Patients

Patients may voluntarily withdraw from the study at any time. If the withdrawal occurs during the treatment period in which the IP is in the patient's bladder, the patient should contact the study site to schedule a visit for IP removal. If a patient exits the study prior to completion, all Exit Visit assessments should be performed at the time of exit.

Notification of early patient discontinuation from the study and the reason for discontinuation will be made to Allergan and will be clearly documented on the appropriate eCRF.

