8.8 Withdrawal Criteria

Patients have the right to withdraw from the study at any time and for any reason without prejudice to his or her future medical care by the physician or the institution. The investigator and Allergan also have the right to withdraw a patient from the study at any time for any reason.

Patients should be discontinued from the study if any of the following criteria are met:

- patient develops (or has an exacerbation of) any medical condition that, in the opinion of the investigator, would put the patient at an unacceptable medical risk or compromises the patient's ability to participate in the study
- patient becomes pregnant (see Section 4.5.1.1 for Definition of Females of Childbearing Potential and Acceptable Contraceptive Methods)
- patient is unwilling or unable to continue to comply with study procedures

Where possible, the decision to withdraw a patient from study treatment or the study should be discussed with Allergan.

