11.0 EFFICACY ANALYSES

The efficacy analyses will be primarily based on the mITT Population with selected tables being repeated using the PP population. Unless stated otherwise, baseline for efficacy is defined as the last non-missing efficacy assessment prior to first Treatment 1 IP insertion. All statistical tests will be 1-sided hypothesis tests performed at the 5% level of significance for main effects. All confidence intervals will be 2-sided 90% confidence intervals, unless stated otherwise.

11.1 **PRIMARY EFFICACY PARAMETER(S)**

The primary efficacy measure is the 7-day mean of the average daily bladder pain NRS (See Section 17.2.1 for definition of average daily bladder pain score).

The primary efficacy variable is the change from baseline to Week 4 Follow-Up post removal of the last IP in Treatment 1 period, using the 7-day mean of the average daily bladder pain NRS score. Patients are scheduled to have two IP insertion in Treatment 1 period and then a Week 4 Follow-Up visit. However, if a patients receives only one IP insertion in the study and has Week 4 Follow-Up assessment, it will be considered in the analysis.

The baseline 7-day mean daily average NRS score will be derived using the diary information from Day -7 to Day -1. In contrast, for patients that receive two IP insertion, the Week 4 Follow-Up mean 7-day average daily pain score will be derived from data collected from Day 50 to Day 56 from date of 1nd IP insertion or Day 36 to Day 42 for patients that receive just one insertion during Treatment 1 period. The mean baseline NRS will be derived if there are at least *any* 5 consecutive valid assessments within the 7-day assessment window (i.e., for baseline it would be day -7 to day -1). If the data that is available is for less than 5 consecutive days, as described above, then the value will be considered missing for that patient. Similarly, the Week 4 Follow-Up NRS will be derived if there are at least *any* 5 consecutive valid assessments within the 7-day assessment window (Day 50 to Day 56 for patients that received two insertion or Day 36 to Day 36 to Day 36 to Day 42 for patients that received just one IP in Treatment 1).

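### Read literally, Protocol 6.5.8 withdraws already-treated patients from the study at Day 14, so the Week 4 data that SAP 11.1 plans for one-IP patients would not be collected for them

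*Protocol*

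**What the plan says.** Protocol 6.5.8 sets the timing: "All patients will undergo a cystoscopic examination on the days of Insertion of the IP". The trigger for withdrawal is that "the investigator discovers an abnormality that would prevent the safe placement, indwelling use, or removal of the IP", and the consequence is that "the patient will not receive treatment and will be withdrawn from the study".

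Protocol 5.6.1 makes Day 14 an insertion day: "On the same day, following the 1st IP removal, the 2nd IP (LiRIS 400 mg or LiRIS Placebo) will be inserted". By then the patient is in the primary analysis population, because Protocol 7.1 says "The mITT population will include all patients who were randomized and received at least 1 IP insertion in Treatment 1".

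For anyone who leaves early, Protocol 8.7 says "If a patient exits the study prior to completion, all Exit Visit assessments should be performed at the time of exit". Protocol 6.5.12 runs the daily pain diary only to the day before the Exit Visit. Protocol 7.2.1 and SAP 11.1 allow a missing Week 4 Follow-up value to be replaced only by a valid Week 2 or Week 3 Follow-up value.

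The SAP expects data from patients who stop after one device. Section 11.1 says "if a patients receives only one IP insertion in the study and has Week 4 Follow-Up assessment, it will be considered in the analysis" and gives them a window of Day 36 to Day 42. Section 17.2.1 adds that their follow-up visits run from the removal of that one IP.

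Protocol 8.8 opens its list with "Patients should be discontinued from the study if any of the following criteria are met". Its closing sentence distinguishes withdrawal from study treatment from withdrawal from the study. Section 6.5.8 does not use that distinction.

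**The concern.** A rule about whether a second device can be inserted also ends data collection. At Day 0 that does no harm to the primary analysis: a patient who never receives an IP is outside the mITT population. At Day 14 the patient has been randomised and treated, and the reason for leaving is a bladder finding made after randomisation and after up to 14 days with a device in place. Protocol 6.5.8 itself names a stone as an example.

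The outcome is then missing for a reason that may be related to how the patient is doing. The primary ANCOVA moves towards a comparison of patients whose bladder remained suitable for a second device. The analyses planned alongside it do not fully repair this. The no-imputation and per-protocol ANCOVAs omit the same patients. The MMRM in SAP 11.1.1 uses their weekly means from before withdrawal, but it assumes the data are missing at random, which is doubtful when a cystoscopic finding causes the exit.

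**Working it through.** **1. What happens to a patient withdrawn at Day 14**

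- First IP inserted on Day 0: she meets the mITT definition (Protocol 7.1).
- Day 14 cystoscopy meets the 6.5.8 trigger: no second IP, and withdrawal from the study.
- Exit assessments take place at exit (8.7), and the diary stops the day before (6.5.12). With exit on Day 14, the last diary day is Day 13.
- The SAP Week 4 window for one-IP patients ends on Day 14 + 28 = 42 and covers Days 36 to 42. Stepping back one week at a time, Week 3 would be Days 29 to 35 and Week 2 Days 22 to 28. (The SAP's weekly window table is not readable in the copy reviewed, so these two windows are inferred from the Week 4 one.)
- All three windows fall after the diary has ended. There is no Week 4 value, no value to impute from, and no contribution to the primary ANCOVA. At the Week 4 comparison her data enter only through the MMRM.

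**2. The plan's own figures**

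Inputs from Protocol 7.7: 36 versus 18 evaluable, difference 1.152, SD 1.67, 1-sided 0.05, 5% not evaluable.

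- Standard error: 1.67 × √(1/36 + 1/18) = 0.482. Noncentrality: 1.152 / 0.482 = 2.39 on 52 degrees of freedom.
- Power from the noncentral t: 76.2%, against 76% stated. This reproduces.
- Enrolment: 72 / 0.95 = 75.8, so 76. The allowance is 76 × 5% = 3.8, about 4 patients across all three arms.

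**3. Power if more patients are lost (counts assumed)**

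| Evaluable, active vs placebo | Power |
|---|---|
| 36 vs 18 (plan) | 76.2% |
| 34 vs 18 | 75.5% |
| 32 vs 18 | 74.6% |
| 32 vs 16 | 71.7% |

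**4. Bias if the loss is related to outcome**

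Let a share p of an arm be withdrawn, and let their mean change be k NRS points worse than that of the patients who stay, whose mean is m. The full-arm mean is (1 − p)m + p(m + k) = m + pk, so the observed arm mean is too favourable by pk. The bias in the treatment difference is p_active × k_active − p_placebo × k_placebo.

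The documents give neither p nor k. Taking k = 2 for illustration:

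| Active lost | Placebo lost | Bias in difference | Share of 1.152 |
|---|---|---|---|
| 2 of 38 | 0 of 19 | 2/38 × 2 = 0.11 | 9% |
| 4 of 38 | 0 of 19 | 4/38 × 2 = 0.21 | 18% |
| 2 of 38 | 1 of 19 | 0.105 − 0.105 = 0 | 0% |

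The third row is the case in which the device alone causes the finding, at the same rate and with the same outcome in both arms.

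**The case against.** **The rule may have been meant for Day 0 only.** The withdrawal sentence comes straight after the one on confirming lesions at Day 0, and denying treatment most naturally describes someone not yet treated. Removal visits, Day 14 included, have their own brief safety cystoscopy with no withdrawal rule. This is a fair reading, so the Day 14 consequence is the literal reading, not the only one. But the authors name Day 0 explicitly when they restrict the lesion check to it, and they place no such limit on the withdrawal sentence. If Day 0 was intended, Day 14 has no stated rule and the text still needs correcting.

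**The plan does provide for one-IP patients.** SAP 11.1 and 17.2.1 do so, and Protocol 5.6.3 orders premature removal of the IP without ordering study withdrawal. This stands: it would be wrong to say the documents never foresee follow-up after a single IP. It also shows that such follow-up was wanted, which is why 6.5.8 conflicts with it.

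**A reader might infer that many patients would be lost, or that the result would be tilted towards active treatment.** The documents support neither. The trigger is an abnormality that makes device use unsafe, not any abnormality, and no rate is given. Active and placebo IPs share the same silicone and nitinol device, so a pure device effect falls on both arms.

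**A reader might also infer that safety follow-up stops at exit.** It does not. Protocol 9.2 requires appropriate follow-up of adverse events ongoing at exit. Section 9.3 requires serious events to be reported for at least 28 days after the last IP and followed to outcome. The narrower point is that the readable text describes no scheduled contact after exit to support this. The visit schedule tables are not readable in the copy reviewed, so that cannot be checked fully.

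**Conclusion.** The point holds as an avoidable gap in data collection. On its literal wording, 6.5.8 prevents collection of the Week 4 value that SAP 11.1 is set up to use, for treated mITT patients whose Day 14 cystoscopy meets the trigger. The loss depends on a finding after randomisation and is not repaired by the imputation rule.

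Its size is unknown and probably modest. Power stays within about two percentage points of the planned 76% for two to four active-arm losses beyond those already allowed for. Bias in the treatment difference requires loss or outcome to differ between arms. The illustrative 0.11 to 0.21 NRS points rest on active-arm losses only and an assumed 2-point deficit, and with equal loss and equal outcome the bias is about zero. The same sentence also covers the Treatment 2 insertion, but that comes after the primary timepoint and does not affect the primary analysis.

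A correction is still worthwhile because it costs little and the control arm has only 18 evaluable patients.

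**What to change.** Reconcile Protocol 6.5.8 with SAP 11.1 and 17.2.1 on data collection only.

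- Leave the decision not to insert an IP exactly as it is.
- Keep withdrawal from the study for Day 0 patients who never received an IP.
- Add to 6.5.8 that a patient who has already received an IP and is given no further IP continues the daily pain diary and safety contacts through Week 4 after the last IP removal, unless she withdraws consent.
- Leave the clinical criteria in 8.8, including pregnancy, unchanged. Ask the sponsor to clarify there, using its existing distinction between leaving study treatment and leaving the study, when diary and safety data are still collected.

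The cost is a wording amendment and off-treatment follow-up of a few patients, who already hold the electronic diary. In return, the SAP's one-IP window can be used for the patients it was written for.
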